2.1.2 Pediatric Labeling of Guanfacine

Adult: Guanfacine immediate release (GIR) is FDA approved for the management of hypertension. It may be given alone or in combination with other antihypertensive agents, especially thiazide-type diuretics.

Pediatric: Included on the GIR label: Safety and effectiveness in children under 12 years of age have not been demonstrated. There is no specific information included regarding the use for ADHD/hyperactivity, inattention, or impulsivity. Adverse reactions noted with guanfacine hydrochloride are similar to those of other drugs of the central α 2-adrenoreceptor agonist class: dry mouth, sedation (somnolence), weakness (asthenia), dizziness, constipation, and impotence. While the reactions are common, most are mild and tend to disappear on continued dosing. Adverse events (AEs) reported in post marketing at an incidence greater than 1% included dry mouth, dizziness, somnolence, fatigue, headache, and nausea.³²

There have been spontaneous post-marketing reports of mania and aggressive behavioral changes in pediatric patients with ADHD receiving GIR tablets. The reported cases were from a single center. All patients had medical or family risk factors for bipolar disorder. All patients recovered upon discontinuation of guanfacine tablets. Hallucinations have been reported in pediatric patients receiving guanfacine tablets for treatment of ADHD.

Included in the label for GER: INTUNIV® is indicated for the treatment of ADHD as monotherapy and as adjunctive therapy to stimulant medications. INTUNIV® was studied for the treatment of ADHD in three controlled monotherapy clinical trials (up to 8 weeks in duration) and one controlled adjunctive trial with psychostimulants (8 weeks in duration) in children and adolescents ages 6-17 who met DSM-IV® criteria for ADHD. The effectiveness of INTUNIV® for longer-term use (more than 8 weeks) has not been systematically evaluated in controlled trials.

2.2 Scientific Rationale

As mentioned in Section 2.1.1, one study has shown that guanfacine is effective and tolerated in children with DS.⁶ While the aforementioned study demonstrated preliminary data, it was limited by the fact that it was open-label, did not include a randomized placebo group, and did not

include scheduled dose increases or follow-ups. To date, there are no randomized, masked, placebo-controlled studies of any ADHD medication in children with DS. This is a significant gap in care for these individuals for a number of reasons: 1) This is a high-risk population for ADHD, with 2) inherent challenges using FDA-approved formulations, and 3) specific comorbidities that make them a uniquely vulnerable population for both the diagnosis and treatment of ADHD.³³ Trials to evaluate drug efficacy and safety coupled with drug exposure data are desperately needed to ensure safe and effective dosing in children with DS.

2.3 Potential Benefits

The use of GIR in this population may result in improved hyperactivity measures, including irritability in participants who are randomized to study drug; however, it is unknown if there will be a benefit to the participant for being in this study. Nonetheless, by sharing the study data and specimens (via NICHD's Data and Specimen Hub (DASH)), children in the future may benefit.

2.4 Known Potential Risks

2.4.1 Risks of Blood Drawing

It is possible that the participant will feel discomfort during the blood draw. It is also possible there will be bruising, swelling or bleeding where the needle enters the skin. The participant may also feel dizzy or a little light-headed when blood is drawn. Every effort should be made to avoid non-standard-of-care draw/sticks for this study and to time clinical blood draws with timed study specimens.

2.4.2 Risks of Guanfacine Hydrochloride

Adverse reactions associated with guanfacine hydrochloride include:

- Dry mouth
- Sedation (somnolence)
- Weakness (asthenia)
- Dizziness
- Constipation
- Impotence
- Decreased HR
- Decreased BP

Most reactions are mild and typically disappear after continued dosing.

2.4.3 Potential Risk of Loss of Confidentiality

There is a potential risk of loss of confidentiality. Every effort will be made to protect the participant's confidential medical information, but this cannot be guaranteed.

2.4.4 Unforeseen Risks

There may be other risks to the participant from this research that are not known or foreseeable at this time.

3 OBJECTIVES AND OUTCOME MEASURES

	Objectives	Outcome Measure(s)	Endpoint(s)
Primary Objective:	Determine efficacy of GIR for the treatment of hyperactivity/impulsivity and inattention in children with DS after 8 weeks of treatment.	Primary Efficacy Outcome Measure: Parent-rated ABC-H subscale score Secondary Efficacy Outcome Measure: CGI-I specific to hyperactivity, inattention and impulsivity behaviors	Primary Endpoint: Change from baseline to Week 8 of the ABC-H subscale score Secondary Efficacy Endpoints: Change from baseline to Week 4 of the ABC-H subscale score. Proportion of participants with a CGI-I score of 2 or better at Week 4 and Week 8.
Secondary Objective:	Characterize the safety profile of GIR in children with DS.	
 • Adverse Events (AEs) • Serious Adverse Events (SAEs) • Safety Events of Special Interest (ESIs) 	Incidence of AEs, SAEs, and safety ESIs through Week 8
Exploratory Objective 1:	Characterize GIR exposure in children with DS.	Guanfacine HCl plasma concentration	Guanfacine HCl exposure at Week 4 and Week 8 as indicated by the following endpoints: 
 • Steady state peak drug concentration ($C_{max,ss}$) • Time at peak concentration ($T_{max,ss}$) • Minimum concentration ($C_{min,ss}$) • Apparent area under the concentration versus time curve at steady state (AUC_{ss}/F) • Apparent clearance (CL_{ss}/F) • Volume of distribution (V/F) • Half-life ($t_{1/2}$)
Exploratory Objective 2:	Characterize the exposure-response relationship of GIR for the treatment of hyperactivity/impulsivity, inattention, and sleep quality in children with DS.	
 • Guanfacine HCl plasma concentrations ($C_{max,ss}$ and $C_{min,ss}$) • Area under the concentration time curve (AUC_{ss}) • ABC-H subscale score • CGI-I • Epworth Sleepiness Scale for Children and Adolescents (ESS-CHAD) • Child's Sleep Habits Questionnaire (CSHQ) 	Change in behavioral and sleep scales (ABC-H, CGI-I, ESS-CHAD, and CSHQ) relative to Guanfacine HCl plasma concentration ($C_{max,ss}$ and $C_{min,ss}$) and AUC_{ss} at Week 4 and Week 8

4 STUDY DESIGN

4.1 Overall Design

A prospective, multi-center, randomized, double-masked, placebo-controlled, flexibly-dosed trial.

4.2 Study Design

4.2.1 Randomization

Participants will be randomized 2:1 to GIR or placebo.

4.2.2 Masking/Unmasking

A masked pharmacist or designee will dispense study product according to randomization treatment assignments. All other site staff as well as participants and parents/legal guardians will also be masked for up to 8 weeks while the study participant is receiving study product. Participants, parents/legal guardians, site staff, and study administrators will be unmasked at the 8 week study visit. Emergency unmasking may occur at any time throughout the study in the event that knowledge of the actual treatment is absolutely essential for further management of the participant. Refer to Section [4.4](#) below and to the Manual of Procedures (MOP) for details.

Unmasking at the 8-week visit is necessary to maintain ethical practice as guanfacine is a commercially available product, and it would be unethical to wean a study participant off of guanfacine if they and their treating clinician determine that it is best for them to maintain treatment outside of the study.

4.3 Study Intervention

Investigational, non-marketed, guanfacine hydrochloride immediate release (GIR) 0.5 mg capsules and matching placebo capsules.

4.4 Duration of Participant Participation

Participants will undergo a screening period of up to 29 days. Eligible participants will receive GIR for up to 8 weeks plus a bridge or taper period, or placebo for up to 8 weeks. The treatment period will consist of study product administration from day 0 through day 56 with a masked dose-escalation period from day 0 through day 49. Unmasking of participant and site staff will occur after the week 8, in-person assessment, Day 56 (\pm 3 days).

After unmasking, participants who were randomized to receive placebo will have a final telephone safety assessment 5 (+ 2) days after final study dose is administered.

After unmasking, participants who were randomized to receive GIR will be given the option to 1) remain on GIR and to transition to open-label GIR per standard of care or 2) taper off of GIR. If the participant, in consultation with their clinical provider, chooses to remain on open-label GIR via standard of care, participants will have enough study product to allow for a 7-day bridge of manufactured GIR study drug to allow time to receive the routine clinical prescription of non-study provided GIR. A final telephone safety assessment will occur 5 (+ 2) days after final manufactured GIR study dose is administered. Alternatively, if the participant, in consultation with their clinical provider, chooses to discontinue GIR, a manufactured GIR taper will be instructed to proceed by a decrease of 1 mg every 3 days (maximum 6 day duration, depending on final study dose) to minimize rebound hypertension. A final telephone safety assessment will occur 5 (+ 2) days after the final manufactured GIR study dose is administered.

4.5 Biological Specimen Collection

Blood will be collected at the Week 4 and Week 8 visits for PK analysis and lab assessments.

4.6 Biological Specimen Retention Plan

See Section [11](#).

4.7 Safety

All AEs, SAEs, and safety ESIs will be collected from the time of first study product administration through the end of study participation.

4.8 Scientific Rationale for Study Design

A randomized, double-masked, placebo-controlled trial will minimize bias and control for confounders. A 2:1 randomization will be used to improve recruitment capacity as parent representatives have indicated that it would be more desirable to enroll their children on a trial that has a greater probability of receiving study drug versus placebo. This was particularly important due to guanfacine being commercially available. Participants will be given an FDA cleared device for parent/legal guardian to measure HR and BP remotely. These assessments will be evaluated prior to each dose escalation. A guided dose-escalation will be used; however, investigators or their designee have flexibility to maintain or decrease a dose based on safety and/or efficacy assessments. Prior networks have utilized a guided dose escalation strategy based on clinical effect and tolerance, similar to dose escalation in clinical practice. This trial will prove the feasibility of masking and randomization, and obtain requisite plasma samples to allow measurement of drug exposure.

4.9 Rationale for Dose Selection

The recommended initial dose of GIR tablets for hypertension when given alone or in combination with another antihypertensive drug is 1 mg daily given at bedtime to minimize somnolence. If after 3 to 4 weeks of therapy 1 mg does not give a satisfactory result, a dose of 2 mg may be given. The current labeled dose range for GER is 0.05-0.08 mg/kg/day, with higher doses of 0.12 mg/kg once daily potentially offering additional benefit. A recommended dosing range for GER is 1 to 4 mg once daily.

Dose escalation plans were created for children ≥ 25 kg, based on previous studies in IDD children who were treated with guanfacine,¹⁴ and were further refined by experts in the clinical care of children with DS. A starting dose of 0.5 mg at bedtime was determined to be the safest starting dose in children weighing ≥ 25 kg. Limiting the participants to children ≥ 25 kg was decided to allow for the safest dose-escalation plan of 0.5 mg increments. Details of the dose escalation plan are shown in [Table 3](#). Prior to each dose escalation assessment, parent/legal guardian will be asked to measure HR and BP using the device given to them from the study team at the time of randomization. The maximum dose will be 3 mg daily, which is below the highest tolerated dose (4 mg daily for GER) in children aged 6-12 years old and ≥ 25 kg. This maximum dose was selected by experts in the field based on clinical practice, which dictates that if symptoms are not manageable with 3 mg daily, the patient is taken off GIR or an additional therapeutic agent is added. This dose range is within the dose range used in studies of neurotypical children aged 6-12 years of age as referenced on the INTUNIV® (GER) label.

Currently, there are no pharmacokinetic (PK) data for GIR specific to children with DS, and although significant differences in drug disposition are not expected, there is no evidence to confirm that the exposure of guanfacine in DS is similar to neurotypical children.

4.10 Study Definition of Enrollment into Active Study

Study enrollment into Active Study is defined as participant has provided informed consent, met all eligibility criteria, and is randomized.

4.11 Study Definition of Completion

Study completion is defined as the last enrolled participant has completed the Final Telephone Safety Assessment 5 (+ 2) days after completion of study product.

Each participant will reach study completion after they have completed the Final Telephone Safety Assessment 5 (+ 2) days after completion of study product or all assessments required for Early Study Withdrawal if they withdraw from the study early (Section **6.6**).

5 STUDY POPULATION

5.1 Selection of the Study Population

A total of 60 eligible participants will be enrolled on this study.

5.2 Inclusion/Exclusion Criteria

Inclusion Criteria	
1. Parent/Legal Guardian can understand the consent process and is willing to provide informed consent/HIPAA authorization prior to the conduct of any study-related procedures. When applicable, the minor participant is willing to provide assent.2. Participant has clinical diagnosis of non-mosaic DS.3. Participant is between 6 and 12 years of age (inclusive) at time of consent.4. Participant weight is ≥ 25 kg.5. Participant has clinically significant symptoms of hyperactivity, inattention and impulsivity manifested as minimum scores of the following rating scales within 30 days of randomization:
a. A minimum score of 18 on the parent-reported ABC-H subscale, ANDb. A minimum score of moderate or greater (≥ 4) on the clinician reported Clinical Global Impression Severity (CGI-S) score specific to hyperactivity, inattention and impulsivity behaviors.6. Participant has co-morbid medical screening and clearance to proceed with a non-stimulant medication trial with GIR within 30 days of randomization.7. Participant is willing and able to comply with study procedures, including adherence to medication dosing schedule.
Exclusion Criteria	
1. Participant has received guanfacine (any formulation) within 30 days of randomization.2. Participant has received any of the following concomitant medication classes within 30 days of randomization:
a. Strong CYP3A4 inhibitors (e.g., boceprevir, clarithromycin, conivaptan, grapefruit juice, indinavir, itraconazole, ketoconazole, lopinavir/ritonavir, mibepradil, nefazodone, nelfinavir, posaconazole, ritonavir, saquinavir, telaprevir, telithromycin, and voriconazole)b. Strong CYP3A4 inducers (e.g., avasimibe, carbamazepine, phenytoin, rifampin, and St. John's wort)3. Participant has a psychiatric comorbidity, such as major depressive disorder, bipolar disorder, obsessive-compulsive disorder, or a psychotic disorder, that requires a pharmacological treatment other than guanfacine.

	
4. For participants \geq 8 years old at the time of consent, participant has a history of suicidality or positive screen on Ask Suicide-Screening Questions (asQ) Tool.5. Participant is currently in or plans to participate in another interventional study.6. Participant has a known hypersensitivity to guanfacine.7. Participant has had a previous guanfacine treatment failure, as determined by their primary treating physician.8. Participant has had a change in another medication intended to treat symptoms of hyperactivity, inattention, and impulsivity within the last 2 weeks.9. Participant has had a seizure within the last 6 months.10. Participant has had a change in their anti-convulsant dose within the last 4 weeks.11. Participant has a cardiac-related condition including:
a. Significant symptomatic bradycardia;b. 2nd degree or 3rd degree (complete) heart block;c. Baseline heart rate (HR) or systolic blood pressure (BP) $>$ 2 standard deviations (SD) below mean for age as determined by medical examination;d. History of aborted sudden cardiac death, unexplained syncope or near syncope, or historical use of a pacemaker as determined by medical history will require clearance by cardiology prior to enrollment;e. Known history of congenital heart disease which requires ongoing care for monitoring or management will require clearance by cardiology prior to enrollment.12. Participant has a history of untreated severe obstructive sleep apnea defined as obstructive apnea hypopnea index (OAHI) \geq 10 events per hour or aortic regurgitation (AR). Participants with an OAHI index $>$ 10/hr are eligible if managed with continuous positive airway pressure (CPAP).13. Participant has untreated thyroid disease.14. Participant has a known hepatic impairment defined as aspartate aminotransferase (AST) or alanine aminotransferase (ALT) $>$ 2x the upper limit of normal (ULN) for age.15. Participant has known impending or renal failure defined as:
a. Anuria diagnosed within 12 hours prior to enrollment;b. Requiring renal replacement therapy.16. Participant is pregnant (refer to Section 7.6.1).17. Participant has any condition which would make the participant, in the opinion of the investigator, unsuitable for the study.
--	---

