Prescribing guidelines report differences in pharmacokinetics and exposure between GIR and GER, and note that a dose substitution on a milligram for milligram basis will result in differences in exposure (INTUNIV® label).²⁶ GIR is 80% bioavailable and the relative bioavailability of GER tablets to GIR tablets is 58%. Compared to GIR, the Area Under the

Curve (AUC) and maximum serum concentration (Cmax) of GER tablets are 43% and 60% lower, respectively. Peak plasma concentrations occur 1 to 4 (average 2.6) hours after a single oral dose of GIR in adults and adolescents with hypertension and 5 hours after oral administration of extended-release tablets to children and adolescents with ADHD. However, studies have found that similar pharmacokinetics can be achieved between formulations. For example, plasma trough concentrations were similar in adults treated for smoking cessation with 3 mg/day administered BID of GIR and 4 mg/day of GER (3 mg/day GIR: M=3.40 ng/mL, standard error (SE) 0.34 vs. 4 mg/day GER: M=3.46 ng/mL, SE=0.67) with similar safety profiles between formulations.²⁹

The GER formulation is a practical challenge to prescribe in children with DS because the pill cannot be crushed and must be swallowed whole, and children with DS are at a high risk for comorbid dysphagia and swallowing dysfunction that puts them at significant risk for aspiration.³⁰ Safely swallowing tablets is a challenge. Children with DS have also been shown to have high risk for sleep apnea and baseline diminished blood pressure profiles compared to age-matched controls,³¹ thus this elevates the safety concerns for sedation and hypotension as known side effects that could be prolonged with an extended release formulation. As such, providers are using GIR to treat ADHD in children with DS in clinical practice with dosing strategies guided by the monitoring of side effects as doses are escalated. No formal dosing guidance exists for this population.

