6.8 Dose Escalation Assessments

Every 5 (+ 2) days through Week 7, just prior to each dose escalation assessment, parent/legal guardian will be asked to measure HR and BP using the device given to them from the study team at the time of randomization. A telephone or in-person assessment by the treating clinician will occur to determine dose escalation. If the participant reaches the maximum dose of 3 mg/day, prior to Week 7, no dose escalation will occur. Alternatively, a CGI-I will be determined by the treating clinician and any score of 3 or worse (higher) will warrant dose escalation, provided no significant safety concerns exist. AEs and safety ESIs will be recorded to assess safety.

Clinically significant findings that would prevent dose escalation include, but are not limited to:

- CGI-I score of 2 or 1
- HR and BP values that are considered unsafe to dose escalate:
 - Clinically significant hypotension, defined as systolic BP percentile less than the 5th percentile.^{31,34} This corresponds to systolic BP percentiles for neurotypical children under the 8th percentile for males and under the 10th percentile for females.
 - Clinically significant bradycardia, defined as HR > 2 SD below mean for age
- Any AEs or safety ESIs that make it unsafe to dose escalate, at the discretion of the treating clinician
- Any other finding that indicates it is not safe to dose escalate, at the discretion of the treating physician and/or principal investigator (PI).

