7.1.2 Safety Events of Special Interest (ESIs)

A safety ESI is a select safety event that could be related to the study drug. Safety ESIs will be solicited for their occurrence (No or Yes) at weekly dose-escalation assessments, including in-person assessments (Week 4 and Week 8), and the final telephone safety assessment (5 + 2 days) after the final dose of study drug. The safety ESIs documented will be assessed by the investigator/delegate (defined as a clinician licensed to make a diagnosis) for intensity, causality, and association to provide uniform data collection of all events. Any reported ESIs should be managed, as needed, according to clinical judgement and local guidelines.

Safety ESIs include:

- Syncope/passing out
- Sedation
- Trouble falling asleep
- Trouble staying asleep
- Trouble waking up
- Drowsiness
- Decreased Energy/Fatigue
- Trouble concentrating
- Trouble breathing
- Constipation
- Diarrhea
- Nausea
- Vomiting
- Skin rash
- Itching
- Change in appetite
- Anxious/fearful

- Sadness/depressed mood
- Self-injurious behavior
- Clinically significant hypotension, defined as systolic BP percentile less than the 5th percentile.^{31,34} This corresponds to systolic BP percentiles for neurotypical children under the 8th percentile for males and under the 10th percentile for females.
- Clinically significant bradycardia, defined as HR > 2 SD below mean for age

The following safety ESIs will only be assessed at in-person visits (Week 4 and Week 8):

- Any clinically significant cardiac event (e.g., clinically significant changes on ECG)
- Suicidality via the asQ Tool (see Section [6.10](#))

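### A child can pass the systolic blood pressure entry limit while already meeting the hypotension limit that stops escalation and counts as a safety event, and the percentile mapping of that limit needs checking against its source.

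*Combined protocol and SAP*

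**What the plan says.** **Entry.** Exclusion 11c, in the synopsis and in Section 5.2, removes a child whose baseline heart rate or systolic pressure is more than 2 "standard deviations (SD) below mean for age as determined by medical examination". The population that supplies the mean and SD is not named.

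**Escalation stop.** Section 6.8 lists among the findings that prevent escalation: "Clinically significant hypotension, defined as systolic BP percentile less than the 5th percentile". It adds: "This corresponds to systolic BP percentiles for neurotypical children under the 8th percentile for males and under the 10th percentile for females".

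**Safety event.** Section 7.1.2 repeats this definition in its list of safety events of special interest (ESIs), including the neurotypical equivalent, "under the 8th percentile for males and under the 10th percentile for females". Neither section asks for a fall from the child's own baseline.

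**Heart rate.** The stop and event limit is "Clinically significant bradycardia, defined as HR > 2 SD below mean for age", which is the same 2 SD used at entry.

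**Background.** Section 2.1.1 says that children with DS have "baseline diminished blood pressure profiles compared to age-matched controls", and gives this as a reason for concern about hypotension.

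**Analysis.** ESIs are solicited as yes or no (Section 7.1.2), are not reported separately as adverse events unless serious (Section 7.5), and are summarised as incidence by arm, with further models adjusted for baseline covariates that are not listed (Section 10.4.2).

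**The concern.** Two things look wrong.

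First, the entry limit lies further into the lower tail than the event limit. Children between the two are admitted, but at an unchanged pressure they satisfy the definition of clinically significant hypotension from the first assessment onward. They can then be held from escalation, and recorded with a hypotension ESI, in either arm and without any effect of study product. Safety is the secondary objective, and the protocol itself singles out hypotension, so an event count that mixes pre-existing with new low pressure is less informative than it should be.

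Second, if pressures in DS are lower, one would expect the DS 5th percentile to sit at or below the neurotypical 5th. The plan puts it at the 8th or 10th.

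**Working it through.** **Inputs from the protocol.** Entry limit 2 SD below the mean (5.2). Event and stop limit at the 5th percentile, stated neurotypical equivalents 8th (males) and 10th (females) (6.8, 7.1.2). Enrolment of 60 (5.1).

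**Assumptions.** Normally distributed systolic pressure. Where a DS shift is used, the DS mean is d SD below the neurotypical mean with equal spread. The documents give no mean or SD for either population, so d is illustrative.

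**1. Limits on one scale.** Φ(−2.00) = 0.0228, the 2.3rd percentile. The 5th, 8th and 10th percentiles are z = −1.645, −1.405 and −1.282. All three lie above −2.00, so the band between entry and event limit is not empty.

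**2. Size of the band with no DS shift.** Share among children who pass entry = (q − 0.0228)/(1 − 0.0228).

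| Event limit q | Share | If it applied to all 60 |
|---|---|---|
| 0.05 | 0.0272/0.9772 = 2.8% | 1.7 |
| 0.08 (males) | 0.0572/0.9772 = 5.9% | 3.5 |
| 0.10 (females) | 0.0772/0.9772 = 7.9% | 4.7 |

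This gives about 2 to 5 of 60.

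**3. Both limits on neurotypical norms, d = 0.3.** On the DS scale entry moves to z = −1.7 (Φ = 0.0446). The event limits move to z = −1.105 (Φ = 0.1346) and −0.982 (Φ = 0.1632).
- Males: (0.1346 − 0.0446)/0.9554 = 9.4%, or 5.7 of 60.
- Females: (0.1632 − 0.0446)/0.9554 = 12.4%, or 7.4 of 60.
- Equal numbers of each sex: (5.7 + 7.4)/2, about 6.5 of 60.

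**4. Entry on neurotypical norms, event limit at the true DS 5th percentile, d = 0.3.** (0.0500 − 0.0446)/0.9554 = 0.6%, or 0.3 of 60. The band closes completely once d exceeds 2.000 − 1.645 = 0.355.

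Steps 2 to 4 give roughly 0 to 7 of 60. This is a range over the cases worked, not a bound: with d = 0.5 the reading in step 3 gives 12.4% (males) and 16.1% (females), or 7.5 and 9.7 of 60.

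**5. The mapping.** It cannot be reproduced from the documents; only its direction can be tested. With equal spread, the DS 5th percentile falls at neurotypical Φ(−1.645 − d).
- d = 0.2: 3.3rd percentile. d = 0.3: 2.6th. d = 0.5: 1.6th. All are below the 5th.
- To reach the 8th or 10th with equal spread, DS pressure would have to be higher by 1.645 − 1.405 = 0.24 SD or 1.645 − 1.282 = 0.36 SD.
- With DS lower by 0.3 SD, the stated mapping needs a DS-to-neurotypical SD ratio of (1.405 − 0.3)/1.645 = 0.67 (males) or (1.282 − 0.3)/1.645 = 0.60 (females).

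**The case against.** The best defence is that entry, escalation and event limits serve different purposes, so a more cautious escalation limit than entry limit is not in itself a contradiction. The protocol history shows that the heart rate and blood pressure criteria were added to escalation deliberately. That stands, and it rules out calling the gap an oversight. It does not explain why a state present before dosing should count as an on-treatment event.

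Other safeguards exist. Inclusion 6 requires medical clearance, exclusion 17 allows investigator judgement, a clinician assesses each ESI for causality, Section 10.4.2 plans covariate-adjusted models, and Section 10.4 defers detail to a statistical analysis plan due before data lock. These can reduce the problem: the gap means that a child can pass, not that such a child will be enrolled. None of them mentions this limit, names baseline pressure as a covariate, or defines a new event.

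A reader might infer that the 8th/10th mapping is reversed. The reverse mapping would indeed fit DS pressures lower by 0.24 and 0.36 SD with equal spread. But the protocol cites sources for the definition that are not available here, Section 2.1.1 does not say that the systolic 5th percentile is lower, and a narrower DS spread would rescue the stated figures. This is a query, not an error shown. The two questions also interact: if the mapping is wrong and entry uses neurotypical norms, the gap can nearly vanish (step 4).

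A reader might also infer a diluted efficacy contrast. Nothing here quantifies one. On the shares of 2.8% to about 11%, some 1 to 4 of the 40 children expected on guanfacine would be affected. They would still receive study product, pressure is re-measured every 5 (+ 2) days, and extreme low readings tend to move back up. Randomisation balances pre-existing low pressure in expectation, so the result is noise rather than bias.

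**Conclusion.** The point holds in a limited form. As written, exclusion 11c admits children who already meet the hypotension definition in Sections 6.8 and 7.1.2, and the heart rate limits do not share this feature. How many depends on reference populations that the protocol does not name. All counts assume normality and enrolled children who follow an otherwise unscreened distribution; the DS shift behind the wider range is an assumption.

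The consequence that can be defended is that pre-existing low pressure can enter the hypotension ESI count in either arm and blur the comparison. A material loss of efficacy information is not shown. The mapping is open: its direction sits awkwardly with Section 2.1.1 unless the DS spread is much narrower, and only the cited sources can decide. Both matters should be settled, but neither undermines the trial.

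**What to change.** **Protocol.** Reconcile Section 5.2 (11c, and its copy in the synopsis) with Sections 6.8 and 7.1.2. Name the reference population for each limit, and verify the 8th/10th percentile equivalents against the cited sources. Which limit is right is for the sponsor and its clinical advisers.

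**Statistical analysis plan.**
- Present hypotension ESIs by arm for all participants.
- Present them also split by whether the Day 1 pre-dose reading already met the definition, and treat as new only events in children who did not meet it on Day 1.
- For children who did meet it on Day 1, report change from Day 1 systolic pressure by arm, so that real falls on treatment are not hidden by the classification.

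Bradycardia needs no parallel rule on this ground, because its entry and event limits agree.

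**Cost.** A text clarification and one extra table. No new measurement is needed, since vital signs are already taken on Day 1 before study product (Table 1, Section 6.3). The drawback is that a site reading on Day 1 is compared with home-device readings later, so the split will misclassify some children; the table should say so.
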